# 13 STATISTICAL CONSIDERATIONS

# 13.1 Statistical Design

#### 13.1.1 Phase I

- This is a dose finding study using the classic 3 + 3 design with fixed dose increments.
- The primary outcome measure is to identify the safe recommended phase II dose using CTCAE version 4.0 criteria to assess dose limiting toxicity.
- The expected number of patients in phase I will be 12.

#### 13.1.2 Phase II

- This is a single-arm study requiring 25 patients.
- The primary outcome measure is the objective response using ACTG criteria following up to 6 cycles of treatment (see Appendix 1).
- A Simon two stage minimax design (Early Phase Clinical Trials Software Version 1.0b) was used.
- The hypothesis (Ha) under investigation is that the recommended phase II dose will produce an objective response in more than 30% of patients.
- The null hypothesis ( $H_0$ ) is that the recommended phase II dose will produce an objective response in less than 10% of patients.
- Stage 1 of accrual: 16 response evaluable patients will be entered in the first stage. Using response hypotheses as stated above, we would reject the drug at the end of the first stage of accrual if only 1 or less objective responses were seen. Otherwise, an additional 9 patients will be accrued.
- Stage 2 of accrual: An additional 9 patients will be accrued. We would accept the drug as active if 5 or more objective responses were observed from the 25 patients accrued.
- Significance level and power: The significance level is set at 0.10 (i.e. the probability of incorrectly rejecting H0 given it is true) and the power is set at 0.90 (i.e. the probability of correctly deciding the regimen is active given the true response rate is greater than 30%).

# 13.2 Statistical Analysis

#### 13.2.1 Phase I

Phase I consists of a dose finding study in the classic 3 + 3 design with fixed dose increments. Phase I data from monotherapy studies of selumetinib enable an initial dose estimate close to the MTD. The expected number of patients recruited to phase I is 12.

- A descriptive analysis will be undertaken to describe toxicity per cycle and dose intensity.
- Non compartmental analysis will estimate Cmax, AUC0-24, clearance and t1/2 from peripheral blood measurements of both AZD6244 and its metabolites.
- Percentage changes in anti-retroviral drug levels will be calculated.
- Percentage inhibition of pERK in tumour tissue will be calculated and correlated with tumour response. Changes to downstream proteins, apoptotic pathways and adaptive changes to other MAPK pathways will be assessed.
- Percentage changes in serum angiogenic markers will be calculated and correlated with tumour response.
- Percentage changes in HIV-viral load and CD4 count will be calculated.
- Response rate will be estimated with 90% confidence intervals.

 Number of treatment cycles completed, duration of response and progression free survival at 6 months from commencing treatment will be reported.

#### 13.2.2 Phase II

Phase II will investigate the efficacy of selumetinib in combination with HAART in patients with KS. Patients recruited to the recommended phase II dose in phase I will be included in phase II.

In order to keep the trial the trial size as small as possible a Simon two-stage design will be used for patient accrual.

Phase II will accrue up to a total of 25 response evaluable patients (including those from phase I). The primary outcome measure of phase II is best objective tumour response up to the end of the 6th cycle. Objective tumour response is as defined by the ACTG criteria (refer to appendix 1 for details). Both CR and PR will count as responses for the purpose of the primary outcome.

- Response rate will be estimated with 90% confidence intervals.
- Toxicity per cycle and dose intensity will be reported.
- Number of treatment cycles completed, duration of response and progression free survival at 6 months from commencing treatment will be reported
- Percentage inhibition of pERK in tumour tissue will be calculated and correlated with tumour response. Changes to downstream proteins, apoptotic pathways and adaptive changes to other MAPK pathways will be assessed.
- Percentage changes in serum angiogenic markers will be calculated and correlated with tumour response.
- Percentage changes in HIV-viral load and CD4 count will be calculated.

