# 1.5.2 Justification for design

Selumetinib has been tested in a number of phase I and phase II trials as both monotherapy and combined with cytotoxic chemotherapy in patients with advanced solid malignancies. A toxicity profile and recommended dose has been established in these patients. Selumetinib has not been tested in combination with HAART. No significant interactions are predicted between selumetinib and HAART however a phase I study is required to investigate the pharmacokinetic effects of combining these drugs. In particular we wish to establish that selumetinib will not reduce the efficacy of HAART. An accelerated phase I trial is proposed commencing at 1 dose level below that recommended for monotherapy or in combination with cytotoxic chemotherapy. Evidence of efficacy will be collected by objective response rate in an open label single arm phase II study. Evidence of efficacy will be used to develop a protocol for a future randomised phase II/III study.

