#### 2.2.2 Phase I & II

- Toxicity assessed by CTCAE v 4.0 criteria (see Appendix 4).
- Number of selumetinib cycles completed and PFS data will be collected as supportive data out to
   12 months from the last patient completing study treatment.
- Objective response rates assessed using ACTG criteria (see Appendix 1).
- Progression free survival rate 6 months from the start of study treatment assessed using ACTG criteria.
- Human immunodeficiency virus (HIV) control by HIV-1 viral load pre-treatment and weeks 3, 6, 12 and 18, and CD4 counts pre-treatment and at weeks 9 and 18.
- Pharmacodynamic measures of selumetinib in combination with HAART assessed by:
  - Serum concentrations of angiogenesis markers including serum Ang-2, IL-6 and VEGF assessed by ELISA pre-study and on weeks 3, 6, 12 and 18.
  - Biopsies pre-study and at week 6 to assess pERK levels in tumour tissue and other downstream markers including c-myc, c-fos, changes in apoptosis markers such as Bad and Bcl-2, and adaptive changes in PI3K/Akt and other MAPK pathways such as JNK and p38.
- Analysis of peripheral blood mononuclear cells (PBMCs) collected in a sub-study at selected centres pre-treatment and at weeks 9 and 18.
  - Levels of pERK, down-stream targets c-fos and c-myc, and key apoptotic proteins Bad and Bcl-2 will be assessed by Western blotting of lysed viable PBMCs.
  - PBMCs will be challenged with TLR4 and 9 agonists and production of IL-1 $\beta$ , TNF- $\alpha$ , IL-6, IL-10, IL-12 and type 1 interferon will be measured by cytometric bead array of culture supernatants.
  - o ROS production by PBMCs will be measured by flow cytometry using dichlorofluorescein (DCF) and cell survival assessed by Annexin V-PE/TO-PRO3 staining and flow cytometry.

Page 18 of 61

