#### 3.1.1.3 HIV control

- The study subjects' HAART PK drug levels, HIV viral load and CD4 counts will be made available to their principal investigator and HIV physician immediately following analysis. Detrimental changes in HIV control considered at least possibly related to the study drug must be discussed with the trial management team HIV physician ([name]) and chief investigator ([name]). Persistent increases in HIV viral load above 200 copies/ml and/or clinically significant decreases in CD4 count will result in the subject discontinuing the study drug.
- As an early phase clinical trial with specific pharmacokinetic and pharmacodynamic endpoints, it is important that patients' HAART regimen is not be changed for their first 3 months on the trial (i.e. until after the C4D22/C5D1 visit) unless clinically necessary.

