# 4 ELIGIBILITY

### 4.1 Inclusion Criteria

- HIV positive and established on a HAART regimen for ≥ 3 months.
- · Histologically confirmed KS
- Measurable disease according to ACTG criteria.
- Progressive cutaneous or nodal KS not requiring chemotherapy OR progressive KS following cytotoxic chemotherapy.
- Evidence of disease progression in the past 6 months. No anti-cancer treatment within one month prior to commencing trial treatment.
- Adequate haematological function:
  - o Haemoglobin ≥ 9 g/dL
  - Absolute neutrophil count ≥ 1.5 x 10^9/L
  - o Platelets ≥ 100 x 10^9/L
- Adequate hepatic function:
  - Serum bilirubin ≤ 1.5 x upper limit of normal (ULN), except if the patient is established on the anti-retroviral drug atazanavir (no upper limit) and has AST and ALT levels ≤ 2.5 x ULN
  - ALT ≤ 2.5 x ULN
  - o AST ≤ 2.5 x ULN
- Adequate renal function:
  - o Serum creatinine clearance > 50 ml/min (Cockcroft-Gault formula or 24 hour urine collection).
- Age ≥ 18 years.
- World Health Organisation (WHO) performance status ≤ 2.
- For selumetinib, women of child bearing age and child bearing potential MUST have a negative
  pregnancy test prior to study entry AND be using an adequate contraception method, which must
  be continued while on treatment and for at least 4 weeks after the study treatment has ended.
- Male patients must agree to use an effective contraception method while on treatment and for at least 16 weeks after the study treatment has ended (barrier contraception is recommended for all individuals living with HIV).
- Written informed consent.

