### 4.2 Exclusion Criteria

- HIV viral load > 200 copies/ml.
- Active opportunistic infections.
- · Active hepatitis B, hepatitis C.
- Any prior exposure to MEK, Ras, or Raf inhibitors or history of hypersensitivity to selumetinib, or any excipient agents.
- Any unresolved toxicity > CTCAE Grade 2 from previous anti-cancer therapy, except for alopecia
- Cardiac conditions as follows:
  - Uncontrolled hypertension (BP ≥150/95 mmHg despite medical therapy)
  - Left ventricular ejection fraction <55% measured by echocardiography

  - o Atrial fibrillation with a ventricular rate >100 bpm on ECG at rest
  - Symptomatic heart failure (NYHA grade II-IV)
  - Prior or current cardiomyopathy
  - Severe valvular heart disease
  - Uncontrolled angina (Canadian Cardiovascular Society grade II-IV despite medical therapy)
  - o Acute coronary syndrome within 6 months prior to starting treatment
- Major surgery within 4 weeks prior to starting selumetinib.
- Refractory nausea, vomiting, chronic gastrointestinal diseases (e.g. inflammatory bowel disease) or significant bowel resection that would preclude adequate absorption.

- Ophthalmological conditions as follows:
  - Intra-ocular pressure >21 mmHg, or uncontrolled glaucoma (irrespective of intra-ocular pressure)
  - Current or past history of central serous retinopathy or retinal vein occlusion
- Evidence of any psychological, familial, sociological or geographical condition potentially hampering protocol compliance.
- Treatment with any investigational product within 28 days of registration.
- Clinical judgement by the Investigator that the patient should not participate in the study.
- Pregnant or breast-feeding women.

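### Viral load is summarised only as percentage change, which is ill-defined at undetectable baselines and does not follow the protocol's own 200 copies/ml criterion

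*Protocol*

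**What the plan says.** The Phase II analysis section (13.2.2) states: "Percentage changes in HIV-viral load and CD4 count will be calculated". Section 13.2.1 says the same for Phase I. Neither adds a log scale, a proportion of patients suppressed, or a rule for results below the assay limit.

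The population is fixed by two eligibility criteria. Section 4.1 requires patients to be "HIV positive and established on a HAART regimen for ≥ 3 months", and section 4.2 excludes "HIV viral load > 200 copies/ml". Section 2.2.2 lists HIV control as an outcome measure for both phases: "control by HIV-1 viral load pre-treatment and weeks 3, 6, 12 and 18", together with CD4 counts. Section 7.9.2.2 adds viral load at the end of every 3 cycles for patients who continue beyond cycle 6.

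Section 3.1.1.3 states loss of control in absolute terms: "Persistent increases in HIV viral load above 200 copies/ml and/or clinically significant decreases in CD4 count will result in the subject discontinuing the study drug". Section 1.5.2 gives the motive: "In particular we wish to establish that selumetinib will not reduce the efficacy of HAART". The other direct look at HAART is in Phase I: "Percentage changes in anti-retroviral drug levels will be calculated" (section 13.2.1). Section 8.3.2 confines pharmacokinetic work to Phase I.

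**The concern.** A percentage change needs a baseline well away from zero. Here eligibility pushes baselines towards zero, from undetectable up to 200 copies/ml. For an undetectable baseline the ratio is undefined, or is set by whatever number replaces the missing value. For a low but quantifiable baseline, a small absolute movement becomes a large percentage.

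The scale also differs from the one the protocol uses to judge harm. Section 3.1.1.3 looks at whether viral load stays above 200 copies/ml. A percentage does not order patients by that criterion.

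The question has substance in this trial. Section 1.3 describes selumetinib as a weak CYP3A inducer, and section 1.4 describes efavirenz as metabolised by CYP3A. Since drug levels are measured in Phase I only, viral load is the one virological measure in Phase II. If it is reported only as percentages, the trial report may show large figures with no virological meaning and may not state how many patients crossed the protocol's threshold.

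**Working it through.** **The plan's design figure.** The protocol's only sample-size calculation is the Simon minimax design in section 13.1.2, which concerns tumour response. The probability of declaring activity at response rate p is the sum, over first-stage responses x from 2 to 16, of P(X1 = x | 16, p) × P(X2 ≥ 5 − x | 9, p). This gives 0.0951 at p = 0.10 (limit 0.10) and 0.903 at p = 0.30 (target 0.90). A search for the smallest maximum sample size returns the same design: stop at 1 or fewer of 16, accept at 5 or more of 25. The design reproduces and does not depend on viral load. There is no design figure for viral load to reproduce.

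**Inputs.** Entry limit 200 copies/ml (section 4.2); threshold for loss of control, persistent values above 200 copies/ml (section 3.1.1.3); planned summary, percentage change (sections 13.2.1 and 13.2.2). The protocol gives no assay limit, so limits of 20, 40 and 50 copies/ml are assumed for illustration.

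**Formula.** Percentage change = 100 × (follow-up − baseline) / baseline.

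**Step 1: undetectable baseline, follow-up 60 copies/ml (still under 200).** With a baseline of 0 the denominator is zero. With substitution:

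| Assumed limit | Substituted value | Percentage change |
|---|---|---|
| 50 | 50 (limit) | 100 × 10/50 = +20% |
| 50 | 25 (half) | 100 × 35/25 = +140% |
| 40 | 40 (limit) | 100 × 20/40 = +50% |
| 40 | 20 (half) | 100 × 40/20 = +200% |
| 20 | 20 (limit) | 100 × 40/20 = +200% |
| 20 | 10 (half) | 100 × 50/10 = +500% |

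One observed result therefore runs from +20% to +500%, and the convention alone decides where it falls.

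**Step 2: quantifiable baseline.**

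| Baseline → follow-up (copies/ml) | Percentage change | Above 200? |
|---|---|---|
| 40 → 190 | 100 × 150/40 = +375% | no |
| 20 → 60 | 100 × 40/20 = +200% | no |
| 190 → 210 | 100 × 20/190 = +10.5% | yes |
| 200 → 201 | 100 × 1/200 = +0.5% | yes |
| 100 → 10,000 | 100 × 9,900/100 = +9900% | yes |

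The first and third rows reverse the order: the larger percentage belongs to the patient whose control is kept. No substitution rule changes this, because both baselines are quantifiable. A crossing at one visit is not yet a persistent excess, so the third and fourth rows show the threshold crossed, not the protocol's criterion met. The last row shows that a large rebound remains visible.

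**Step 3: what a threshold summary would give.** The proportion above 200 copies/ml is defined for every patient with a follow-up value, whatever the baseline. Exact (Clopper-Pearson) 90% intervals with 25 patients:

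- 0 of 25 above 200: 0% to 11.3% (25/25 at or below: 88.7% to 100%)
- 1 of 25 above 200: 0.2% to 17.6% (24/25: 82.4% to 99.8%)
- 2 of 25 above 200: 1.4% to 23.1% (23/25: 76.9% to 98.6%)

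**The case against.** The strongest reply is that this is one descriptive variable and that a statistical analysis plan, not shown here, may settle how values below the limit are handled. It is fair to leave substitution rules, log scales and censoring to such a plan. But the choice of percentage change is made in the protocol itself, and step 2 shows a mismatch that no substitution rule repairs.

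A reader might infer that the trial cannot show whether HAART keeps its effect, or that percentage change in viral load is the only Phase II measure bearing on it. The protocol does not support either reading. CD4 count is analysed in both phases. Section 3.1.1.3 applies an absolute threshold to each patient, and section 10.1 provides a form for the date and reason of discontinuation. A gross rebound from a quantifiable baseline would be obvious. Patients treated at the recommended dose in Phase I count in Phase II, and drug levels were planned for them.

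Nor does anything in the protocol say that undetectable patients would be dropped and failures thereby hidden. The sentence in section 1.5.2 about HAART efficacy follows one about Phase I pharmacokinetics, so it should not be read as a formal Phase II hypothesis.

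The CD4 part of the planned sentence is not at fault: a CD4 count has no zero-baseline problem in practice.

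**Conclusion.** The point holds within limits. Percentage change is a poor scale for viral load in this population, for two separate reasons: it is undefined or convention-driven at undetectable baselines (+20% to +500% for the same follow-up of 60 copies/ml), and it does not follow the protocol's own criterion (+375% with control kept against +10.5% with the threshold crossed).

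The first figure rests on assumed assay limits of 20 to 50 copies/ml and substitution at the limit or half of it. The number of patients affected is unknown, because the protocol gives neither the limit nor the share with undetectable baselines. Section 7.9.1 measures viral load at screening and again on day 1, so a day 1 baseline slightly above 200 copies/ml is not ruled out; this does not alter the argument.

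The consequence is limited to how a descriptive outcome is reported. The primary endpoint, the Simon design and the handling of individual patients are unaffected. Correction is still worthwhile, because the outcome bears on a question the protocol says it cares about and the better summary costs almost nothing.

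**What to change.** In sections 13.2.1 and 13.2.2, replace percentage change in viral load by the following:

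- The number and proportion of patients, with exact 90% interval, with any on-treatment viral load above 200 copies/ml.
- Separately, the number and proportion with persistent excess, defined for reporting as above 200 copies/ml at two consecutive available measurements. No confirmatory repeat is scheduled, so an excess at the last visit with no later value should be reported as unconfirmed.
- All scheduled values should be used: weeks 3, 6, 12 and 18, and those every 3 cycles in continuing patients.
- Individual values should be shown on a log10 scale, with results below the assay limit marked as censored.

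Leave the CD4 summary as it is.

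This is a reporting summary built on the threshold already in section 3.1.1.3, and it changes no clinical rule. The cost is one sentence in each of the two sections. No new samples or visits are needed.

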#### 14 TRIAL ORGANISATIONAL STRUCTURE

# 14.1 Sponsor

The sponsor of this trial is the Sheffield Teaching Hospitals NHS Foundation Trust.

### 14.2 Coordinating Centre

The trial is being conducted under the auspices of the CRCTU, University of Birmingham according to their local procedures.

### 14.3 Trial Management Group (TMG)

The TMG will consist of the Chief Investigator, Co-Investigators, Trial Co-ordinator and Statistician. The TMG will be responsible for the clinical set-up, on-going management, promotion of the study, and for the interpretation of the results.

#### 14.4 Safety Review Committee

The Safety Review Committee will consist of the Chief Investigator, Co-Investigators, other trial investigators from recruitment centres and the trial team at CRCTU. After completion of each cohort, there will be a teleconference between all Principal Investigators and the CI to discuss toxicity levels, adverse events etc.

#### 14.5 Data Monitoring Committee

A Data Monitoring Committee (DMC) will be established to assess any safety issues and will report to the Trial Management Group. The DMC will convene annually.

#### 14.6 Finance

This is a clinician-initiated and clinician-led trial funded by Cancer Research UK together with a grant from AstraZeneca. AstraZeneca will be providing selumetinib free of charge.

#### 15 ETHICAL CONSIDERATIONS

The trial will be performed in accordance with the recommendations guiding physicians in biomedical research involving human subjects, adopted by the 18th World Medical Association General Assembly, Helsinki, Finland, June 1964, amended at the 48th World Medical Association General Assembly, Somerset West, Republic of South Africa, October 1996 (See **Appendix 2**).

(website: http://www.wma.net/en/30publications/10policies/b3/index.html).

The trial will be conducted in accordance with the Research Governance Framework for Health and Social Care, the applicable UK Statutory Instruments, (which include the Medicines for Human Use Clinical Trials 2004 and subsequent amendments and the Data Protection Act 1998 and Human Tissue Act 2008) and the principles of GCP. This trial will be carried out under a Clinical Trial Authorisation in accordance with the Medicines for Human Use Clinical Trials regulations. The protocol will be submitted to and approved by the main REC prior to circulation.

Before any patients are enrolled into the trial, the Principal Investigator at each site is required to obtain local R&D approval. Sites will not be permitted to enrol patients until written confirmation of R&D approval is received by the Trial Office. It is the responsibility of the Principal Investigator to ensure that all subsequent amendments gain the necessary local approval. This does not affect the individual clinicians' responsibility to take immediate action if thought necessary to protect the health and interest of individual patients.

# 16 CONFIDENTIALITY AND DATA PROTECTION

Personal data recorded on all documents will be regarded as strictly confidential and will be handled and stored in accordance with the Data Protection Act 1998. With the patient's consent, their full name, date of birth, National Health Service (NHS) number, or in Scotland the Community Health Index (CHI), address, post code, hospital number, general practitioner details will be collected at trial entry to assist with long-term follow-up via other health care professionals (e.g. patient's GP). Patients will be identified using only their unique registration number, initials and date of birth on the Case Report Form and correspondence between the Trial Office and the participating site. However patients are asked to give permission for the Trial Office to be sent a copy of their signed Informed Consent Form which will not be anonymised. This will be used to perform in-house monitoring of the consent process and may also be forwarded to other health care professionals involved in the treatment of the patient (e.g. patient's GP).

The Investigator must maintain documents not for submission to the Trial Office (e.g. Patient Identification Logs) in strict confidence. In the case of specific issues and/or queries from the regulatory authorities, it will be necessary to have access to the complete trial records, provided that patient confidentiality is protected.

The Trial Office will maintain the confidentiality of all patients' data and will not disclose information by which patients may be identified to any third party. Representatives of the SCART trial team may be required to have access to patient's notes for quality assurance purposes but patients should be reassured that their confidentiality will be respected at all times.

